SOCIAL PROTOCOL (HRP-580)

PROTOCOL TITLE:

VERSION DATE:

ANCILLARY REVIEWS

DO NOT DELETE. Submit the completed checklist below with your protocol.

Which ancillary reviews do I need and when do I need them?			
Select yes or no	Does your study...	If yes...	Impact on IRB Review
 Yes  No	Include Gillette resources, staff or locations	Gillette Scientific review and Gillette Research Administration approval is required. Contact: [contact]	Required prior to IRB submission
 Yes  No	Involve Epic, or Fairview patients, staff, locations, or resources?	The Fairview ancillary review will be assigned to your study by IRB staff Contact: [contact]	Approval must be received prior to IRB committee / designated review.
 Yes  No	Include evaluation of drugs, devices, biologics, tobacco, or dietary supplements or data subject to FDA inspection?	STOP – Complete the Medical Template Protocol (HRP-590) The regulatory ancillary review will be assigned to your study by IRB staff Contact: [contact] See https://policy.umn.edu/research/individual	Consider seeking approval prior to IRB submission .
 Yes  No	Require Scientific Review? Not sure? See guidance in the Investigator Manual (HRP-103).	ONLY REQUIRED BIOMEDICAL RESEARCH REVIEWED BY FULL COMMITTEE	
 Yes  No	Relate to cancer patients, cancer treatments, cancer screening/prevention, or tobacco?	Complete the CPRC application process. Contact: [contact]	
 Yes  No	Include the use of radiation? (x-ray imaging, radiopharmaceuticals, external beam or brachytherapy)	Complete the AURPC Human Use Application and follow instructions on the form for submission to the AURPC committee. Contact: [contact]	Approval from these committees must be received

SOCIAL PROTOCOL (HRP-580)

PROTOCOL TITLE:

VERSION DATE:

 Yes  No	Use the Center for Magnetic Resonance Research (CMRR) as a study location?	Complete the CMRR pre-IRB ancillary review Contact: [contact]	prior to IRB approval; These groups each have their own application process.

1.0 Objectives

1.1 Purpose:

The **primary objective** of this study phase is to test a brief training for PC personnel and a referral process to equip them to effectively refer parents to a brief eHealth parent intervention thereby increasing access to needed services through effective engagement in a trusted setting.

We will evaluate the referral process and conduct a pilot test of the PC personnel training within FQHC clinics. PC personnel (n=35) within two FQHC primary care clinics will be randomly assigned to receive communication skills training or a control condition. Control group personnel will receive a written description of the referral process but no training. Aim a: Using a sequential mixed-methods approach with PC personnel, we will evaluate the acceptability and appropriateness of the referral process and the training. Aim b: We will pilot test the effectiveness of the training to increase PC personnel's communication skills. We will also use EHR data to pilot test the effect of the training on parent engagement in GenPMTO by comparing the referral rates among patients who had an appointment with personnel in the training arm to those seeing control personnel.

[Note that a second arm of this study will examine the effectiveness of the brief, eHealth version of GenPMTO among the referred parents; this study is presented in a separate IRB protocol]

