Pediatric primary care reaches underserved communities. In general, 96% of parents report having a usual place of healthcare,²⁰ and ~53%-90% of children attend their three-year and five-year well-child visit.²¹ Within low-income populations, primary care clinics still reach a large portion of the population; rates of well-child visit attendance at three and five years old have been found to be similar between uninsured families, those with private insurance, and those with public insurance.²¹ Furthermore, about 95% of Minnesota children receive the final Measles Mumps and Rubella (MMR) vaccine before kindergarten,²² indicating that the vast majority of children have contact with primary care before starting kindergarten.

Need for strategies for primary care to effectively engage and refer parents to preventative services. Research shows that typical referral practices are inadequate. First, many pediatric patients and families who would benefit from a referral do not receive one or do not follow through.^{11,23-27} For example, only 26-42% of preschool children with mental health symptoms identified in PC received referrals.²⁸ A number of factors contribute to this, including lack of clear policies and ambiguous roles among referring and specialty personnel.^{29,30} Second, referral completion rates can be improved through targeted efforts, such as technology-enhanced referral tools or training^{26,31-32,33-35} and dedicated personnel for referral tracking and follow up.^{32,36} Third, parent engagement in parenting programs is generally low, but can be improved by targeted engagement efforts.³⁷ Fourth, PC personnel are typically not trained to address behavioral or parenting topics,¹⁰ which requires specific knowledge as well as particular communication skills to address these sensitive topics in ways that are less likely to lead to resistance and defensiveness. This gap in training exists despite the fact that PC personnel are often the first point of contact when parents have concerns about a child's behavior.³⁸⁻³⁹ Finally, implementation scientists have advocated for hybrid trials in which an intervention and an implementation strategy are both tested,⁴⁰ which may speed the delay between research findings and real-world dissemination. Taken together, any effort to deliver parenting programs within a primary care population, in a scalable and effective way, must equip primary care to effectively engage and refer parents.

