3.0 Study Endpoints/Events/Outcomes

3.1 Primary Endpoint/Event/Outcome:

SOCIAL PROTOCOL (HRP-580)

PROTOCOL TITLE:

VERSION DATE:

The primary study outcome is referral rates. Note that parent engagement will also be measured in a separate arm of the study, captured in a separate IRB protocol.

We will also assess acceptability, feasibility, and appropriateness of the training and referral process to PC personnel. Note that the acceptability of the referral process among parents will also be measured in a separate arm of the study, captured in a separate IRB.

3.2 Secondary Endpoint(s)/Event(s)/Outcome(s):

The secondary outcome is PC personnel communication skills.

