4.0 Study Intervention(s)/Interaction(s)

4.1 Description:

Participating providers will be randomly assigned to either a communication skills training and training in the referral process or to receive a written description of the referral process.

Data will be collected in the form of online surveys, audio recorded responses to vignettes, focus groups, and referral counts.

We will develop 5 brief vignettes to measure communication skills related to parent engagement (e.g., “After learning about a parent spanking their child, you decide to raise the topic of discipline; how do you start?”). Verbal responses will be audio-recorded directly in the online survey. Because the communication skills in the PC training will mirror the therapist skills in GenPMTO, we will adapt relevant components of the Fidelity of Implementation Rating System⁴¹ and two coders will rate the quality of response, accounting for confronting, teaching, supporting, and facilitating.

All PC personnel in the study (including control and training conditions) will receive a written summary and process map of the referral process. The referral process will be modeled on an Institute for Healthcare Improvement (IHI) report, which documents a 9-step process for “closing the loop” on referrals. The referral process, in short, is that the medical care provider will make a referral using a designated form, the therapist will confirm receipt and take over responsibility for communication with the family, and the therapist will communicate with PC personnel at specified intervals with specified follow-up steps. PC personnel in both arms of the study will be informed of the referral process because a specified referral process constitutes a minimal implementation step, which should reasonably accompany a new resource; this will allow us to examine the effectiveness of communication skills training (which is also recommended in the IHI report) over and above the referral process.

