The training will focus on communication skills based on key constructs in the Health Belief Model and motivation/resistance research. Research of the Health Belief Model⁴² has shown that perceived benefits and perceived barriers are predictive of participation in preventive services;⁴³ which hold for preventive parenting programs.^{44, 45} For example, parents may not see benefits of prevention programs when children are young. Perceived (and real) barriers to attending parenting programs also adversely impact attendance and must be addressed to engage parents.¹⁶ In addition, studies of parent non-compliance within interventions has shown that when parents feel confronted and taught, the likelihood of resistance to change increases.⁴⁶ This research informs the communication skills therapists learn to use in GenPMTO and will be included in the PC personnel training.⁴⁷ These skills involve conveying information in motivating and supportive ways to facilitate and empower parents to change. The training will focus on: (1) conveying the benefits of parenting programs, (2) knowledge

SOCIAL PROTOCOL (HRP-580)

PROTOCOL TITLE:

VERSION DATE:

of and responses to common perceived barriers to attending parenting programs, and (3) skills and strategies to effectively motivate and refer parents in ways that are least likely to elicit resistance. The training will include a 30-minute online introduction and a 56-60 minute in-person meeting. It will include a theoretical background and experiential learning; each step of the referral process will be demonstrated and role-played.

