5.0 Procedures Involved

5.1 Study Design:

We will use a sequential mixed-methods approach to address the research question: Are the referral process and training acceptable, feasible, and appropriate? We will randomize PC personnel within two FQHC clinics to receive training or to a control group in which they only receive the information on how to refer to therapists who provide eHealth GenPMTO. We will survey the PC personnel in the training and control arms after the training and after the pilot year. We will conduct focus groups with a subset of PC personnel to gain a deeper understanding of survey results. The mixed methods design will be sequential in structure, with the purpose of the qualitative research being to explain and expand on survey results (i.e., QUAN->QUAL).⁴⁸⁻⁵⁰ We will use a small-scale randomized trial to address two pilot effectiveness research questions: Does the PC personnel training have a direct effect on parent engagement? Is there an indirect effect through the mechanism of improved communication skills? We hypothesize that point estimates will indicate such effects.

5.2 Study Procedures:

[figure not shown]
A diagram of the study flow for providers is provided below.

PC personnel will be randomized to the training group or a control group. Personnel in the training group will participate in surveys after the completion of PC personnel training; PC personnel in both training and control group will complete surveys after the year-long pilot study. We will recruit personnel from the training group for a focus group (or interviews if scheduling is a barrier), and personnel from the control group for a focus group (or interviews) after the post-pilot surveys are completed. In addition, we will request aggregate referral rate data from HCMC medical records. For each provider, we will request the number of children ages 2-5 seen during the pilot year and the number of referrals made.

SOCIAL PROTOCOL (HRP-580)

PROTOCOL TITLE:

VERSION DATE:

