17.0 Statistical Considerations

17.1 Data Analysis Plan:

In order to measure communication skills, we will code the audiorecorded responses to vignettes. Because the communication skills in the PC training will mirror the therapist skills in GenPMTO, we will adapt relevant components of the Fidelity of Implementation Rating System⁴¹ and two coders will rate the quality of response, accounting for confronting, teaching, supporting, and facilitating.

We will examine the preliminary effectiveness of the PC personnel training. We hypothesize that communication skills and referral rates, will both be higher in the training group compared to the control group. While this pilot study *is not meant to provide sufficient power for significance testing*, these hypotheses will guide our analyses. We will analyze differences between training and control groups on outcomes including communication skill and referral rates, using generalized linear multivariate regression. We will examine communication skill items individually and assess the psychometrics of the items as a scale and as indicators of a latent variable. Each outcome will be analyzed in a separate model. In the first analysis, we will only enter training condition as a dummy variable (i.e., t-test) to examine between group differences. In subsequent analyses we will include covariates to account for clinical experience and demographic variables. Primary covariates include discipline (i.e., family medicine or pediatrics department) and years of experience. We will also examine differences by clinic location and examine intra-class correlations. These analyses will be useful in guiding focus group topics, examining the usefulness of the survey items we adapt and create, and generating effect size estimates and variance components for a fully-powered trial. Finally, we will examine the indirect effect of the PC personnel training on parent engagement through the mechanism (mediation) of PC personnel communication skills. For mediation analyses, we will use path models in MPlus with bootstrapped indirect effects.

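### Section 1.1 tests parent engagement by comparing referral rates, but this protocol's data support a conclusion about referrals only; the referral-rate denominator also has two age ranges

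*Combined protocol and SAP*

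**What the plan says.** All references are to the combined protocol and SAP.

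- **1.1 Purpose:** "We will also use EHR data to pilot test the effect of the training on parent engagement in GenPMTO by comparing the referral rates". The sentence goes on to assign patients to an arm by the provider they saw.
- **3.1 Primary outcome:** "The primary study outcome is referral rates". It then adds: "Note that parent engagement will also be measured in a separate arm of the study, captured in a separate IRB protocol".
- **5.1 Study Design:** the first pilot effectiveness question is "Does the PC personnel training have a direct effect on parent engagement". The second asks about an indirect effect through communication skills. No data source for engagement is given.
- **5.2 Study Procedures:** the medical-record request is aggregate. For each provider it covers children aged 2-5 seen in the pilot year and referrals made.
- **6.2 Data:** the table lists referral rates and the number of children aged 3-5 seen. It has no engagement row. Section 11.1 also describes the children as three to five years old.
- **8.1 timeline:** referral and engagement appear as two rates to be compared between arms.
- **17.1 Data Analysis Plan:** the between-arm regressions use communication skill and referral rates. The last analysis changes the outcome: "we will examine the indirect effect of the PC personnel training on parent engagement through the mechanism (mediation) of PC personnel communication skills".

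**The concern.** Section 1.1 uses one quantity as the measure of another. The plan itself gives reasons to keep them apart. Section 2.3 notes that "many pediatric patients and families who would benefit from a referral do not receive one or do not follow through", which separates receiving a referral from acting on it. Under 4.1, once a referral is made, "the therapist will confirm receipt and take over responsibility for communication with the family", so what follows is no longer in the referring provider's hands alone.

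If 1.1 were followed as written, a difference in what providers do would be reported as a difference in what parents do. The mediation analysis has a related problem. Its named outcome is not among the data elements listed here, so the variable actually used could be settled after the data are seen. The pilot exists to supply effect sizes and variances for planning a larger trial (11.1, 17.1), so a mislabelled estimate would carry into that design.

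The age range is a separate matter. The number of children seen is the denominator of the primary outcome, and two sections define it differently.

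**Working it through.** The plan gives no figure for engagement or for uptake after referral, so there is nothing on this point to reproduce. The power statements in 17.1 (.47, and .61 one-tailed, for 35 providers and an effect of .66) do reproduce: a noncentral t calculation with 17 and 18 per arm and an assumed alpha of .05 gives 0.474 two-sided and 0.605 one-sided. They are not in question.

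**Step 1. Outcome named against data listed.**

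| Analysis | Outcome named | Listed data that supply it (5.2, 6.2) |
|---|---|---|
| 1.1 record comparison | Engagement, by way of referral rates | Referrals and children seen: referral rate only |
| 17.1 between-arm regression | Referral rates | Yes |
| 5.1 question | Engagement | None listed |
| 17.1 mediation | Engagement | None listed |

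**Step 2. How the two quantities relate.** In one arm,

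engaged families per child seen = (referrals / children seen) × (engaged families / referrals).

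Divide training by control. Write R for the ratio of referral rates and U for the ratio of uptake per referral:

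engagement ratio = R × U.

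The engagement ratio equals R only when U = 1. For R above 1, engagement is still higher under training whenever U exceeds 1/R. The break-even values are 1/1.10 = 0.91, 1/1.20 = 0.83 and 1/2.00 = 0.50.

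**Step 3. Illustration in both directions; every input is assumed.** Take 1,000 children seen per arm, with 100 control and 120 training referrals, so R = 0.120 / 0.100 = 1.20. Let 50 control families start the program, an uptake of 50/100 = 0.500.

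| Assumed U | Training uptake | Training families engaged | Engagement ratio per child seen |
|---|---|---|---|
| 0.83 (= 1/1.20) | 0.417 | 120 × 0.417 = 50 | 50/50 = 1.00 |
| 1.00 | 0.500 | 120 × 0.500 = 60 | 60/50 = 1.20 |
| 1.20 | 0.600 | 120 × 0.600 = 72 | 72/50 = 1.44 |

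The referral comparison reads +20% in every row. Engagement per child seen runs from no difference to +44%.

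**Step 4. Which direction the documents suggest.** Section 4.1 says the training covers "skills and strategies to effectively motivate and refer parents in ways that are least likely to elicit resistance", which points to U above 1; the referral ratio would then understate the engagement effect. Trained providers may also refer a different mix of families, which could push U below 1. The documents give no figure for either.

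**Step 5. The denominator.** Let s be the share of two-year-olds among children aged 2-5 seen. If the referral count stays the same, changing the denominator from 2-5 to 3-5 multiplies the rate by 1/(1 − s). With equal attendance in each of the four years of age (an assumption), s = 1/4 and the factor is 1/0.75 = 1.33. The between-arm ratio is unchanged if s is the same in both arms. Section 5.2 states no age limit for the referral count, so numerator and denominator could also cover different children.

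**The case against.** The strongest reply is that the working sections are already right. Section 3.1 and the 17.1 regression both say referral rates, and 8.1 lists the two quantities separately, so 1.1 is one loose sentence. Engagement is openly assigned to a separate protocol, which may define it and link it to providers. Attribution by arm is clearly intended: 1.1 assigns patients by the provider seen, and 8.1 plans engagement rates by arm. Section 5.2 also mentions referral source counts, a provider referral count form and survey items on parents' responses and declined referrals. Training and skill are provider-level variables, so a provider-level engagement count might be enough. Finally, this is a pilot that disclaims conclusive inference.

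Most of this stands, and it rules out three stronger conclusions that a reader might draw.

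- **That a referral difference says nothing about engagement unless uptake is equal.** Equal uptake is needed for the two ratios to coincide, not for them to point the same way. Step 2 shows how far uptake would have to fall before the engagement gain vanished.
- **That the primary comparison is unsound.** It is correctly labelled in 3.1 and 17.1 and does not use engagement.
- **That families cannot be linked to providers, or that engagement will go unmeasured.** The documents do not show this. The separate protocol is not available here. The NA answer in 18.4 on records to be reviewed is compatible with a request for aggregate counts and says nothing about engagement data held elsewhere.

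The reply leaves three things unanswered: the measure stated in 1.1, an engagement outcome in 5.1 and 17.1 with no stated source, and the two age ranges.

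**Conclusion.** The point holds in a limited form. The 1.1 comparison can support a conclusion about referrals and should not be reported as one about engagement. The 5.1 question and the mediation model need a named outcome that is available. The age-range conflict is a plain contradiction in the denominator of the primary outcome.

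The size of any error from the relabelling cannot be estimated from the documents, and its direction is open. The range in step 3 shows only how the two quantities can part; it predicts nothing about this study. Confidence is high about what this document states and omits. No judgement is possible on the separate protocol. The matter should be corrected, but it does not threaten the pilot: 5.1 hypothesises only about point estimates, and the primary analysis is untouched apart from the age range.

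**What to change.** 1. **Section 1.1:** name the referral rate as the outcome of the record comparison and limit that conclusion to referrals.
2. **Section 5.1 and the 17.1 mediation model:** if it can be obtained, use the separate protocol's count of engaged families by referring provider; define it and cite its source. Analyse it per child seen. The number of referrals is itself affected by arm, so a per-referral analysis would compare groups selected after randomisation. If no such count can be obtained, run the mediation on the referral rate, label it so, and leave the engagement question to the separate protocol.
3. **Sections 5.2 and 6.2:** reconcile the age range so that numerator and denominator of the referral rate cover the same children, and check 11.1 against the result.

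The cost is a wording change in 1.1, a short addition to 5.1 and 17.1, and one reconciliation. The first option in item 2 also needs a provider-level count whose availability this document does not establish. The second needs no new data, but this protocol would then give no engagement answer of its own.

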2.0 Background

2.1 Significance of Research Question/Purpose:

Nearly all effective prevention programs for young children target parenting behaviors as the mechanism of change and they have been shown to prevent behavioral health issues such as depression, anxiety, and conduct disorder.¹⁻⁷ Unfortunately, these programs have extremely limited reach within the population; the programs are not widely available nor well-attended.⁸ Pediatric primary care (PC) is a non-stigmatizing setting with nearly universal reach and, therefore, an ideal access point to increase availability.⁹ However, PC personnel are not trained to address behavioral health topics.¹⁰ Also, typical referral practices are inadequate.¹¹ To impact behavioral health at a population level, there is a significant need to develop effective referral practices to preventative services.¹²⁻¹³ The research proposed here is significant, because we will develop and test a strategy for increasing reach of an evidence-based parenting program through primary care referrals.

2.2 Preliminary Data:

[name] conducted a survey of parents at the same downtown pediatric clinic partnering in this proposed study, finding that 82% of parents were interested in behavioral health resources and were most likely to utilize online resources.¹⁴ He evaluated a pilot of a novel program called Behavior Checker in two safety-net clinics, in which PC personnel reported that having a parenting resource on hand increased efficiency of behavioral health discussions.¹⁵

2.3 Existing Literature:

In a paper co-lead by [name] (PI),⁹ three primary benefits of primary care settings for parenting programs were highlighted: First, primary care may overcome stigma associated with parenting programs.^{16,17} Second, engaging parents through primary care would affiliate the programs with a stable and trusted service provider.¹⁸ Third, stable and sustainable funding

SOCIAL PROTOCOL (HRP-580)

PROTOCOL TITLE:

VERSION DATE:

mechanisms are available for programs delivered in or referred to from primary care. But while disparate funding strategies for these programs do exist,¹⁹ research to demonstrate the effectiveness of the programs within a primary-care population is needed to facilitate more widespread and stable funding under the Affordable Care Act.

Pediatric primary care reaches underserved communities. In general, 96% of parents report having a usual place of healthcare,²⁰ and ~53%-90% of children attend their three-year and five-year well-child visit.²¹ Within low-income populations, primary care clinics still reach a large portion of the population; rates of well-child visit attendance at three and five years old have been found to be similar between uninsured families, those with private insurance, and those with public insurance.²¹ Furthermore, about 95% of Minnesota children receive the final Measles Mumps and Rubella (MMR) vaccine before kindergarten,²² indicating that the vast majority of children have contact with primary care before starting kindergarten.

Need for strategies for primary care to effectively engage and refer parents to preventative services. Research shows that typical referral practices are inadequate. First, many pediatric patients and families who would benefit from a referral do not receive one or do not follow through.^{11,23-27} For example, only 26-42% of preschool children with mental health symptoms identified in PC received referrals.²⁸ A number of factors contribute to this, including lack of clear policies and ambiguous roles among referring and specialty personnel.^{29,30} Second, referral completion rates can be improved through targeted efforts, such as technology-enhanced referral tools or training^{26,31-32,33-35} and dedicated personnel for referral tracking and follow up.^{32,36} Third, parent engagement in parenting programs is generally low, but can be improved by targeted engagement efforts.³⁷ Fourth, PC personnel are typically not trained to address behavioral or parenting topics,¹⁰ which requires specific knowledge as well as particular communication skills to address these sensitive topics in ways that are less likely to lead to resistance and defensiveness. This gap in training exists despite the fact that PC personnel are often the first point of contact when parents have concerns about a child's behavior.³⁸⁻³⁹ Finally, implementation scientists have advocated for hybrid trials in which an intervention and an implementation strategy are both tested,⁴⁰ which may speed the delay between research findings and real-world dissemination. Taken together, any effort to deliver parenting programs within a primary care population, in a scalable and effective way, must equip primary care to effectively engage and refer parents.

This research is significant because it increases reach through targeted engagement, testing a brief training for PC personnel and a referral process to equip them to effectively refer parents to a brief eHealth parent intervention thereby increasing access to needed services through effective engagement in a trusted setting. Successful completion of this research will contribute to more fully realizing the public health benefits of parenting programs, increasing the return on past research investments.

